study arm to receive ketamine 0.3 mg/kg along with ondansetron 4 mg IV. The diphenhydramine or ondansetron will be administered first, and immediately afterward the prochlorperazine or ketamine will be administered. The prochlorperazine or ketamine will be diluted in saline so that the total volume is 5 mL, and will be administered over 2 minutes. The diphenhydramine will be diluted in saline so that it is 2 mL (the same volume as the ondansetron). Both groups will also receive a 500 mL normal saline bolus after the study medications are administered. The ED pharmacist will be responsible for preparing the medications, using a double-blind protocol. He or she will record which arm the patient was randomized to. Only the pharmacist will have access to the randomization records and will not reveal the randomization until the end of the study. Emergency providers will be instructed not to administer any rescue medications for at least 30 minutes. The electronic medical record order will read “randomized study medication” (for the ketamine or prochlorperazine) and “randomized add-on medication” (for the ondansetron or diphenhydramine).

Safety

After 30 minutes, the treating provider will be permitted to administer any medication they would like for further treatment. If there is an untoward event that requires the treating provider to know which medication was administered, the pharmacist will unblind the randomization for that individual patient and the patient will not continue in the study.

Reportable Events

Anticipated side effects are those listed on the manufacturer’s package insert and are treated as routine non-urgent or non-emergent events are not reportable events.

Adverse Events are those unanticipated side effects that require interventions or anticipated side effects that do not respond to intervention.

Serious Adverse Events are those side effects that require Advanced Life Support measures to control symptoms.

AEs and SAEs will be reported to the IRB within 5 days of the event.

Methods of Measurement

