Enrolled patients will fill out a brief data collection form to include age, sex, race, phone number, and baseline headache severity using a 100-mm visual analog scale (VAS). Repeat headache severity scores will be measured at 15, 30, 45, and 60 minutes. Time zero begins immediately after complete administration of the study drug. Nausea (with a 100 m VAS), vomiting, anxiety, restlessness (akathisia), heart rate, and blood pressure will also be assessed at these time intervals. The need for rescue medications will be extracted from the patient’s chart at a later time.

Trained research assistants will call the patient 24-48 hours post-discharge by phone to ask them to rate their satisfaction with the drug they received on a scale of 0-10, and to

ask if they are currently having a headache (yes or no). If the patient is admitted, the patient will be approached in the hospital by an investigator or research assistant for follow up.

Outcome Measures

The primary outcome measure will be the difference in pain scores between the prochlorperazine and ketamine groups, measured as the absolute difference between the means at 60 min. Secondly, we will measure the difference between the rates of decline in pain scores, rate of admission, nausea scores, rate of vomiting, rate of development of akathisia, rate of use of additional medications for headache, heart rate and blood pressure changes, headache resolution with telephone follow up, and patient satisfaction.

Privacy and Security

In order to protect the privacy of the research subjects and to maintain the confidentiality of data, all data will be managed only by trained research assistants or investigators and will be stored in the locked Emergency Medicine research offices and electronic data will be stored on a password protected computer in the locked Emergency Medicine research office. All research assistants and investigators are HIPAA- trained, CITI trained and credentialed by UMC IRB, and oriented to the study protocol.

Data Analysis:

A couple prior studies have used a 25-mm difference in mean VAS score reduction between groups to show a clinical benefit [6,9]. We define significant pain relief as an absolute decrease in the mean VAS score of 25 mm.

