Thirty-two patients will be needed in each group to find a 25-mm difference between the group means on the VAS at 60 min, with a power of 0.80 and an alpha of 0.05. We will aim for 35 patients per group to account for about a 10% dropout rate. The groups will be compared using a *t*-test on gender, race, and age; and a chi (with Yates correction)-squared test on severity of presenting headache, to determine if they are similar. The individual VAS measurements will be compared using a repeated measures analysis of variance (ANOVA) test.

References:

- [3] Cicek M, Karcioğlu O, Parlak I, et al. Prospective, randomised, double blind,

controlled comparison of metoclopramide and pethidine in the emergency treatment of acute primary vascular and tension type headache episodes. *Emerg Med J.* 2004;21:323-326.

[7] Jones J, et al. Randomized double-blind trial of intravenous prochlorperazine for the treatment of acute headache. *JAMA.* 1989;261:1174-1176.

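### The repeated measures ANOVA for the VAS scores has no sphericity correction and no missing-score rule, so its group-by-time test probably rejects too often and usable numbers can fall below 32 per group

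*Combined protocol and SAP*

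**What the plan says.** Under Methods of Measurement, "Repeat headache severity scores will be measured at 15, 30, 45, and 60 minutes", in addition to a baseline score. Outcome Measures defines the primary outcome as the between-group difference in pain scores, "measured as the absolute difference between the means at 60 min". The first secondary outcome is about the shape of the curves: "Secondly, we will measure the difference between the rates of decline in pain scores".

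Data Analysis sizes the trial on the 60-minute means: "Thirty-two patients will be needed in each group to find a 25-mm difference between the group means on the VAS at 60 min". The stated power is 0.80 and the significance level 0.05. The section then adds an allowance: "We will aim for 35 patients per group to account for about a 10% dropout rate". The analysis of the scores is a single sentence: "The individual VAS measurements will be compared using a repeated measures analysis of variance (ANOVA) test".

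The t-test and chi-squared test in the same section only check whether the groups are alike at baseline. The section does not say which ANOVA term tests which outcome, whether baseline counts as a time level, whether the time terms are corrected, or what happens to a patient with a missing score.

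**The concern.** Two default properties of the classical method are weak in this setting.

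**Sphericity.** The F tests for time and group-by-time assume that the differences between every pair of time points have the same variance. Pain scores 15 minutes apart are likely to be more alike than scores 45 minutes apart. The spread may also widen as some patients recover and others do not. When the assumption fails, the uncorrected tests reject too often. The group-by-time term is the natural test of a difference in rates of decline, so that secondary outcome is exposed.

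**Complete rows.** In its standard form the method uses only patients with every score. Someone asleep or in imaging at 30 minutes would be left out even with a valid 60-minute score, and the allowance for loss is only 3 patients per group.

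**Working it through.** **Inputs from the protocol.** Four post-dose scores at 15-minute spacing (five with baseline); 32 patients needed and 35 enrolled per group; a 25-mm difference; power 0.80; alpha 0.05.

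**Assumptions.** The protocol gives no SD, no correlation between scores, no missing-score rate and no sidedness. I took a two-sided test, AR(1) correlation of 0.5 to 0.9 per 15-minute step, SD either constant at 35 mm or rising from 20 to 35 mm, and missed scores independent across times.

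**Step 1: the plan's own figure.** Without an SD, 32 per group can only be solved backwards.
- Normal approximation: n = 2(1.96 + 0.84)² × (SD/25)². Setting n = 32 gives SD = 35.7 mm.
- Exact t-test: the detectable standardised difference at n = 32 is 0.711, so SD = 25/0.711 = 35.1 mm.
- Dropout: 35 × 0.90 = 31.5, so 10% dropout alone uses up the margin. Keeping 32 of 35 allows a loss of 1 − 32/35 = 8.6%.

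**Step 2: error rates with no true difference.** There were 32 patients per group and 40,000 simulated trials per row. The Monte Carlo standard error is √(0.05 × 0.95/40,000), about 0.1 percentage point. GG is the Greenhouse-Geisser correction.

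| Scores | Correlation pattern | Group-by-time, uncorrected | Group-by-time, GG | Group main effect | 60-min two-sample test |
|---|---|---|---|---|---|
| 4 | Equal (0.6), sphericity holds | 5.1% | 4.8% | 4.9% | 5.2% |
| 4 | AR(1) 0.5 | 5.8% | 4.7% | 4.8% | 4.9% |
| 4 | AR(1) 0.7 | 6.6% | 5.0% | 5.0% | 5.2% |
| 4 | AR(1) 0.9 | 6.9% | 4.8% | 5.0% | 5.0% |
| 4 | AR(1) 0.9, rising SD | 7.6% | 4.9% | 5.0% | 5.0% |
| 5 | AR(1) 0.5 | 6.1% | 4.8% | 5.0% | 5.0% |
| 5 | AR(1) 0.9 | 7.9% | 4.8% | 5.0% | 5.0% |
| 5 | AR(1) 0.9, rising SD | 8.7% | 4.7% | 5.0% | 5.0% |

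A repeat at 35 per group with correlations of 0.7 to 0.9 gave 6.5% to 7.7% with four scores and 6.7% to 8.8% with five for the uncorrected test. The corrected test gave 4.5% to 5.3%, and the 60-minute comparison 4.6% to 5.2%.

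**Step 3: complete rows.** If a share m of scores is missed at each of the four post-dose times, the expected number of complete rows is 35 × (1 − m)⁴, before any dropout.
- m = 1%: 33.6
- m = 2%: 32.3
- m = 3%: 31.0
- m = 5%: 28.5

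The number stays at 32 when m = 1 − (32/35)^(1/4) = 2.2%. If baseline also counts as a time level, the threshold is 1 − (32/35)^(1/5) = 1.8%.

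**Step 4: what the loss costs.** For a two-sample t-test at 60 minutes with SD 35.1 mm, power is 0.80 at 32 per group, 0.79 at 31 and 0.74 at 28. These figures refer to the primary comparison run on complete rows only, not to the group-by-time test.

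**The case against.** The strongest reply is that the primary outcome is safe. It is a difference in means at one time point, the trial is sized on it, and sphericity does not enter a plain 60-minute comparison or the group main effect. That stands. A reader might infer that the trial's primary false-positive rate exceeds 5%. The documents do not support this: it would follow only if the group-by-time F test were the primary test, and the protocol does not say so.

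Second, the size of the inflation depends on assumed correlations. The top figure needs five time levels, correlation 0.9 and a rising SD together. That also stands. With four scores the range is about 6% to 8%.

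Third, the protocol nowhere says that patients with a missed score are dropped. That is the method's default, not a written rule. Nor does the protocol define dropout, so the allowance might be meant to cover missed readings. A reader might conclude that numbers will fall below 32. The documents give no missing rate, and at 1% per score more than 33 remain. The defensible statement is that numbers can fall below 32. It is fair to add that the protocol's own 10% dropout leaves 31.5, and that unblinding is a further route to incomplete rows, since "the pharmacist will unblind the randomization for that individual patient and the patient will not continue in the study".

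Fourth, a reader might infer that complete-row analysis biases the 60-minute difference. One simulation let 30% to 50% of patients below 25 mm at 45 minutes miss the 60-minute score; a true 25 mm was then estimated at about 23.7 to 22.1 mm. That removes the 60-minute score itself, which any simple 60-minute comparison would also lose. It does not show a fault specific to the ANOVA, and I place no weight on it.

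Finally, Greenhouse-Geisser alone restores about 5%. True, but it neither keeps partial rows nor names the primary contrast.

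**Conclusion.** The concern holds in a limited form and is worth acting on because the remedy is cheap. The only method named for the VAS outcome scores leaves open both points on which its defaults are weak.

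- **Error rate.** If correlation decays with time, which is likely at this spacing, the uncorrected group-by-time test runs at about 6% to 8% with four scores and up to about 9% with five. This concerns the rate of decline, a secondary outcome. The group main effect and the plain 60-minute comparison hold 5%. I did not simulate a 60-minute contrast built on the ANOVA's pooled error term.
- **Numbers.** If the default deletion is applied, fewer than 32 per group remain once more than about 2% of scores are missed at each post-dose time, before dropout. The power cost is modest: 0.80 falls to 0.74 at 28 per group, which needs about 5% missed at each time.

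The correlations, SD patterns, missing rates and two-sided test are my assumptions. The weakness does not invalidate the trial.

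**What to change.** Replace the ANOVA sentence in Data Analysis with:

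> VAS scores at 15, 30, 45 and 60 minutes will be analysed by a linear mixed model for repeated measures (REML) with arm, time (categorical), arm-by-time and baseline VAS, unstructured within-patient covariance and Kenward-Roger degrees of freedom, using every available score; the primary test is the arm contrast at 60 minutes, and the arm-by-time test addresses the rate of decline.

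This removes the sphericity assumption, keeps patients with partial data and ties the model to the stated primary outcome. With four post-dose scores, the arm-by-time test compares the curves from 15 to 60 minutes; any difference already present at 15 minutes shows in the arm contrasts. If the ANOVA is kept as a secondary display, report Greenhouse-Geisser-corrected p-values for the time terms.

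The cost is one sentence and standard software, with no new patients or data. There are two downsides. The unstructured matrix has 4 × 5/2 = 10 parameters, a few more than the ANOVA implies. And validity with missing scores rests on a missing-at-random assumption, which the plan should state.
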